## **Abstract**

This study presents the development and validation of a unique Digital Experience Sampling Method (ESM) questionnaire specifically adapted for monitoring changes in the mental state of patients during psychiatric hospitalization. The questionnaire was carefully crafted through focus groups involving patients and clinical staff, ensuring its relevance and applicability to the unique characteristics of mental state changes in a hospitalization setting.

To evaluate the validity of the ESM questionnaire, symptom severity trends obtained from the questionnaire will be compared with estimates derived from the Positive and Negative Syndrome Scale (PANSS) assessment. Data will be collected from 100 subjects over a 14-day psychiatric hospitalization period. In addition to the ESM questionnaire, smartwatch sensors will monitor physiological indicators.

Feasibility and patient compliance will be assessed by examining patients' willingness to use the digital ESM questionnaires and the smartwatch sensors. The study will also cross-reference self-reported sleep quality and activity levels captured in the ESM questionnaires with objective physiological indicators and nursing staff reports, providing insights into the reliability of the patient-reported data.

Furthermore, the study will evaluate the impact of the ESM data on clinical decision-making by physicians throughout the 14-day psychiatric hospitalization period. Patient satisfaction and satisfaction among the multidisciplinary team with the monitoring model will also be assessed.

This research underscores the potential of digital technologies to enhance patient-centered care and facilitate informed treatment decisions in psychiatric hospitalization settings.

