### **Research Process**

The focus groups were held at Sheba Medical Center on 5/18/22, 08/9/22, and 11/09/22. The groups were guided by the researcher and another facilitator, who work as senior clinical psychologists in the psychiatric inpatient wards at the Sheba Medical Center. A professional transcriber attended each group and typed the conversation throughout the focus groups. The transcripts of the discussions in the focus groups were qualitatively analyzed. After collecting and processing the data from the focus group, the ESM questionnaire was improved and refined, considering the findings.

2. **Running the monitoring model - Feasibility and Validity phase** - this phase will begin in the middle of 2023 and is expected to continue for 18 months.

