### **Participants**

To conduct the monitoring model, we will recruit 100 subjects hospitalized in the inpatient wards. To receive feedback on implementing the monitoring model from the multi-disciplinary care team working in the wards, we will recruit 30 multi-disciplinary team members. The running will be carried out in two stages:

- Pre-Test - 20 patients and feedback from 5 multi-disciplinary – estimated time – 3 months.
- Field Test - 80 additional patients and feedback from 30 multi-disciplinary staff members – estimated 12 months.

The study inclusion criteria for the patients: adults are consenting hospitalized in a psychiatric hospital at the Sheba Medical Center in the open part of the ward who owns a mobile smartphone. Exclusion criteria: patients with a low level of treatment compliance, patients with a developmental or intellectual disability, complex organic conditions including dementia, patients who cannot read and write in the Hebrew language, and patients who are incapable of informed consent.

The study inclusion criteria for the multi-disciplinary team: multi-disciplinary team members who work in the psychiatric inpatient wards at the Sheba Medical Center. The staff members will have a valid Israeli license (from the professions of medicine, nursing, psychology, social work, and occupational therapy).

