## **Indices**

### **Pre-test indices –**

1. The process involves selecting ESM questionnaire items based on their distribution indices to ensure optimal item distribution. It also includes refining the wording of items with low variability scores within and between subjects, aiming to enhance their variability.
2. We will evaluate the satisfaction indicators of the clinical staff working in the ward based on the monitoring indicators. If needed, we will enhance the implementation of the monitoring model within the clinical team in the ward.

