### **Field test indices –**

3. The validation of the ESM questionnaire will be conducted by comparing the change trends in the questionnaire indices during a 14-day psychiatric hospitalization period to the change trends in four different measurements of psychiatric symptoms assessed by the PANSS diagnostic tool, which is widely recognized as the gold standard in psychiatric symptom assessment. The subject's assessment using PANSS will be conducted at four different time points:
  - a. T1 - at study entry (day 1)
  - b. T2 - during the first week of the study (between days 4-6)
  - c. T3 - during the second week of the study (between days 10-12)
  - d. T4 - at the end of the study (day 14)
4. Feasibility and compliance:
  - a. The responsiveness to participation in the monitoring model - The number of subjects who agreed to participate in the study out of the subjects we offered to participate.
  - b. The extent of responding to the self-report questionnaires over 14 days multiplied by three times a day.
  - c. The degree of responsiveness to wearing and charging the smartwatch for 14 days.

- d. The degree of difference between subjects with different psychiatric diagnoses (psychotic spectrum, depression, mania, and personality disorders) in their adherence and responsiveness to agree to participate in the study, answer the self-report ESM questionnaires and wear and charge the smartwatch.
- 5. The validity of the subject's ESM self-reports on sleep quality and activity level:
  - a. The validity of the subject's self-reports on sleep quality -The subject's self-reported data about his sleep quality and number of awakenings will be compared to physiological indicators that the smartwatch will collect (number of hours of sleep, number of awakenings) and will be equalized in addition to the medical reports of the nursing staff in the ward.
  - b. The validity of the subject's self-reports on his activity level:  
The subject's self-reported data about his energy and activity level will be compared to physiological indicators that the smartwatch will collect (number of steps, accelerations) and will be equalized in addition to the reports of the nursing staff in the ward.
  - c. The degree of difference between subjects with different psychiatric diagnoses (psychotic spectrum, depression, mania, and personality disorders) in correspondence between the self-report and the physiological indices and the reports of the nursing staff.

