## **Research Process**

After recruiting the patient for the study and signing informed consent, the monitoring application (Datos Health) and the wearable smartwatch application (Garmin) will be installed on the patient's smartphone. The patient will receive an extensive explanation from the research team's representative on the self-reporting method and will experience using the application.

From this stage, the hospitalized subject will receive ongoing clinical care, alongside participation in monitoring indicators by self-reporting in the ESM questionnaires using the Datos Health application and physiological indices monitoring by using the Garmin smartwatch. The trial will end after 14 days or until the patient's discharge (whichever comes first). The ESM self-report sampling will be conducted a frequency of 3 times a day in a semi-random manner:

- The first sample will be randomly sampled between 8-10 am.
- A second sample will be randomly sampled between 1-3 pm.
- A third sample will be randomly sampled between 7-10 pm.

In each clinical discussion of the subject's mental state, the ward staff will watch the dashboard of the Datos Health application, which will display the subject's self-report measures and physiological indicators. For each change in the patient's clinical status, determined by the physician (change of medication, vacation, preparation for discharge, discharge), the physician will answer a questionnaire in which he will document how much (between 1-5) the clinical decision was influenced by the monitoring indicators he observed.

The feasibility and compliance, Validity, and changes in the patient's condition over timeline indicators will be collected for 14 days and analyzed at the study's end. The patient satisfaction indicators will be tested after 14 days of monitoring through a questionnaire sent to each subject. The satisfaction indicators of the clinical staff in the ward will be tested through questionnaires sent to the clinical staff at the end of the study.

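### Does the abstract's figure of 100 subjects contradict a validation carried out in the 80 field-test patients?

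*Protocol*

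**What the plan says.** The abstract gives one sample size. Directly after the sentence on comparing ESM trends with PANSS it states: "Data will be collected from 100 subjects over a 14-day psychiatric hospitalization period". It does not mention stages.

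The Participants section of phase 2 gives the same total and splits it:

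- "Pre-Test - 20 patients and feedback from 5 multi-disciplinary"
- "Field Test - 80 additional patients and feedback from 30 multi-disciplinary staff members"

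The Indices section then gives each stage its tasks. Under the pre-test heading: "The process involves selecting ESM questionnaire items based on their distribution indices to ensure optimal item distribution", followed by "It also includes refining the wording of items with low variability scores within and between subjects, aiming to enhance their variability". The only other pre-test index is staff satisfaction. Under the field-test heading, item 3 reads: "The validation of the ESM questionnaire will be conducted by comparing the change trends in the questionnaire indices", with the four PANSS time points. The sleep and activity comparisons with the smartwatch and nursing reports come under the same heading.

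Two other places bear on the point. Phase 2 as a whole is titled "Running the monitoring model - Feasibility and Validity phase". The phase 2 Research Process says that the feasibility, validity and change "indicators will be collected for 14 days and analyzed at the study's end", without separating the stages.

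**The concern.** The abstract names the PANSS comparison and gives 100 in the next sentence, so it is natural to read 100 as the size of the validation sample. The stage structure in the body gives 80. Validation against PANSS is the primary objective, so its sample should be clear.

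The second worry is pooling. The phase title and the end-of-study analysis sentence both cover the two stages together, and nothing states that the questionnaire is fixed when the pre-test ends or that its 20 patients are left out. If all 100 were analysed together, two problems would follow. Scores from different item sets or wordings would be combined wherever the pre-test had dropped or changed an item. The patients used to choose the items would also be reused to validate them. Rewording aims to raise variability within subjects as well as between them, and a comparison of change trends rests on within-subject variation, so mixing versions could alter the very quantity being validated.

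**Working it through.** **1. The enrolment total.** Inputs: 20 pre-test and 80 further field-test patients, from the Participants section. 20 + 80 = 100. This reproduces the total in that section and in the abstract, so no stated figure is wrong. The pre-test share is 20/100 = 20%.

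**2. What the abstract sentence claims.** It says that data are collected from 100 subjects. It does not say that all 100 enter the PANSS comparison; that link comes only from the sentence before it. The sentence after it turns to smartwatch monitoring, which fits a general account of data collection.

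**3. Which patients the body assigns to validation.**

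| Place | Pre-test (20) | Field test (80) |
|---|---|---|
| Participants, phase 2 | first stage | described as additional patients |
| Indices, items 1–2 | item selection, rewording, staff satisfaction | – |
| Indices, items 3–8 | – | PANSS validation, feasibility and compliance, sleep and activity validity, influence on decisions, patient and team satisfaction |

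The numbering runs on from one heading to the next, so each index is listed under exactly one stage. PANSS validation appears only under the field test, which gives 80.

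**4. Whether the two remaining places propose pooling.** The phase 2 title covers a phase that contains both stages and defines no analysis set. The Research Process sentence gives the timing of analysis. Analysing at the end of the study is compatible with keeping the stages apart.

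**5. Size of the difference, as an illustration only.** The Protocol gives no correlation or precision target. Assume one summary value per patient, no dropout and a between-patient correlation r.

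SE(z) = 1/√(n − 3)

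- n = 80: 1/√77 = 0.114
- n = 100: 1/√97 = 0.102
- ratio: √(97/77) = 1.12

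95% CI = tanh(atanh(r) ± 1.96 × SE):

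| Assumed r | n = 80 | n = 100 |
|---|---|---|
| 0.3 | 0.09 to 0.49 | 0.11 to 0.47 |
| 0.5 | 0.32 to 0.65 | 0.34 to 0.63 |
| 0.7 | 0.57 to 0.80 | 0.58 to 0.79 |

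At r = 0.5 the interval width is 0.334 at 80 and 0.297 at 100. The maximum data volume is 80 × 4 = 320 PANSS assessments against 100 × 4 = 400. With 14 × 3 = 42 prompts per patient, it is 80 × 42 = 3,360 ESM prompts against 100 × 42 = 4,200. The planned analysis compares trends over repeated measurements, so these intervals show only the order of magnitude.

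**The case for a change.** The strongest case for a change is that a section heading is a weak way to define the sample for a primary objective. The abstract lists validation, feasibility, sleep and activity checks, decision impact and satisfaction, and its only sample size is 100, yet the body places all of these under the 80-patient stage. The statement of the primary objective and the specific aims name neither a number nor a stage. Locking an instrument between stages is also study conduct rather than analysis, so it cannot be left wholly to an analysis plan. A sentence or two of text would settle the matter at no cost in patients or visits.

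Part of this stands. A quick reader of the abstract could be misled, and an explicit statement of the lock and of the validation sample would be a harmless courtesy.

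The rest does not carry. The harm depends on pooling, which the Protocol does not propose and its structure points against. A stage called a pre-test, whose task is to settle items before further patients are recruited, already implies that the revised questionnaire is what the field test uses. Even if the 20 were reused, the selection would not be circular: items are chosen on their distributions, not on agreement with PANSS, the smartwatch or nursing reports. Which patients enter which analysis is ordinary content of a statistical analysis plan, and its absence from the Protocol is not an error.

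**Conclusion.** The concern does not call for a change. The 100 in the abstract is the enrolment total and agrees with 20 + 80. The body already separates development on 20 patients from validation on 80 others, which is the separation the concern asks for. Mixed questionnaire versions would be a real problem under pooling, but no text proposes pooling, so no bias is shown. Nor is precision lost, because no validation size of 100 was ever stated. For scale, the Fisher-z standard error at 80 patients is about 12% larger than at 100, on the assumption of a single between-patient correlation and no dropout.

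The conclusion rests on reading the pre-test and field-test headings as assigning each index to its stage, which is their plain sense. What is left is an abstract that omits the stages and an analysis-set detail that analysts would sensibly fill in.

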## Introduction

Assessing the mental state of the patient hospitalized in a psychiatric ward is essential for providing optimal treatment during the hospitalization and determining the recommendations for continued treatment after discharge. This evaluation is mainly based on the assessment of the patient's subjective experience in a variety of aspects (such as mood, thoughts, feelings, and emotional pain) and the evaluation of his/her functioning (such as behavior, social functioning, mental functioning, level of daily activity, sleeping mechanisms, eating). Frequent documentation throughout the day of the patient's self-reports on his condition and function monitoring is rare in routine care in psychiatric inpatient wards, even though the patient's subjective perspective on his mental condition is an integral part of the psychiatric evaluation.

The positive and negative syndrome scale (PANSS) for schizophrenia (Kay et al., 1987) is the "gold standard" medical scale for measuring the severity of symptoms in patients with schizophrenia spectrum disorders. It is conducted through a brief interview rather than a self-report. Several valid assessment tools rely on the patient's self-report of his condition and focus on psychiatric symptoms (PROM - Patient-reported outcome measure), such as (SCL-90) The Symptom Checklist 90 (Derogatis et al., 1973), and The Brief Symptom Inventory (BSI) (Derogatis & Melisaratos, 1983). Many tools focus on specific disorders, such as The Beck Depression Inventory (Beck et al., 1996), to assess depression. Other self-report questionnaires focus on the patient's quality of life, which is also essential for evaluating his psychiatric condition, such as MANSA - the Manchester Short Assessment of Quality of Life (Priebe et al., 1999). Despite the extensive use of self-report questionnaires in research and with outpatients, few valid tools focus on self-report of the mental state of the patient during his hospitalization in the psychiatric ward, such as the BASIS: The Behavior and Symptom Identification Scale (Eisen et al., 1986), focuses on both the presence of symptoms and the monitoring of function.

The patient's report from memory about various symptoms and functional characteristics experienced in a period ranging from a week to a month is typical in these standard tools. These measurement tools are widely used for research purposes. Still, there is difficulty in using them in clinical work within the inpatient ward due to their length, difficulty in allocating personnel to deliver the questionnaire, note and analyze the results, and difficulty in using the collected data as a tool available for the work of the staff in the ward. Due to

these difficulties, few studies use PROMS questionnaires among hospitalized psychiatric patients. With the advancement of technology and the prevalence of smartphones, it became possible to use digital questionnaires to monitor mental states. Wong et al. (2022) described the use of digital PROMS questionnaires to characterize the symptoms and the improvement in the mental state throughout psychiatric hospitalization; this follow-up was carried out at the time of admission to the hospital and at the time of discharge when the standard questionnaires demonstrated an improvement in the mental state of the hospitalized patients. These findings indicated the importance of using self-report questionnaires in the treatment routine throughout psychiatric hospitalization to provide more accurate treatment to hospitalized patients.

There are inherent disadvantages to performing a clinical assessment using standardized questionnaires. Using the patient's memory to record symptoms is prone to biases due to a tendency to remember complex events more strongly and difficulty recalling moments when powerful symptoms were not experienced, or there were no symptoms. In addition, there is difficulty in examining slight changes in the patient's condition, which are often below the sensitivity threshold of the standard tools (Shiffman et al., 2008; Csikszentmihalyi & Larson, 2014).

In the field of psychopathology, there is a growing awareness that the models that describe the psychological experience are dynamic, change over time, and their understanding requires multiple samples and sometimes continuous monitoring while paying attention to the microenvironmental factors that surround the person and influence his condition (Myin-Germeys et al., 2009; Myin-Germeys et al., 2018).

## **Momentary Assessment Strategies**

Momentary assessment strategies use repeated real-time sampling of subjects' behaviors and experiences. The sample can be discrete (e.g., by self-reporting about subjective aspects of the experience at a given moment), continuous (e.g., by continuous monitoring of physiological indicators using sensors), or combined (Varese et al., 2019). The strategies often used are the Experience Sampling Method-ESM (Delespaul, 1995; Hektner et al., 2007) and EMA - Ecological Momentary Assessment (Stone & Shiffman, 1994; Shiffman et al., 2008); both methods will be referred to below as ESM. The ESM is a method Structured based on a diary, in which the subjects are asked to report their thoughts, feelings, and symptoms during their daily life, as well as to describe the context in which the report takes

place, for example, location, social situation, and activity. They can also assess their satisfaction with the current situation that was sampled. ESM is a strategy with significant advantages in research in psychiatry and somatic problems and is the basis for studies in optimizing clinical decisions in these fields (Verhagen et al., 2016). With the development of technology and the frequent use of smartphones, the collection of samples, the analysis of their characteristics, and the use of sensors on mobile phones (Ben-Zeev et al., 2016) became simple and more available for conducting ESM studies. It was also found that the patient's response to electronic diary management is significantly better than using paper and pencil for running a diary (Stone et al., 2003). To assess the validity of the ESM questionnaire for psychiatric symptoms, it is customary to compare the results obtained from standard measures such as the PANSS assessment, widely recognized as the gold standard for evaluating psychiatric symptoms, with the observed changes in symptom evaluation using the ESM questionnaires (Harvey et al., 2021).

### **Use of ESM methodology during psychiatric inpatient stays**

Studies using ESM methodology for ambulatory patients used diverse ESM questionnaires (Csikszentmihalyi & Larson, 2014; Hare et al., 2015; Chen et al., 2016a, 2016b; Wilhelm & Schoebi, 2007). However, those questionnaires are not useful in examining patients' experience in the unique situation of psychiatric hospitalization. For example, questions inquire regarding the description of the current situation, such as, "Where are you?" "Who are you with?" (Csikszentmihalyi & Larson, 2014), which is often unsuitable to ask in a hospital. In addition, it is necessary to refer to the fact that hospitalized patients are in an acute phase of their illness, and their condition should be assessed accordingly. The use of ESM models during psychiatric hospitalization has been tested and found to be feasible and valid (Kimhy et al., 2006; So et al., 2013). Studies have examined momentary changes in the mental state of hospitalized psychiatric patients (Houben et al., 2017; Hallensleben et al., 2029;; Lucht et al., 2022; Brüdern et al., 2022). However, we did not find a study examining the use of the ESM model to support the clinical decisions of the treating staff in the psychiatric ward.

